5.3. Other Considerations for Data Analyses and Data Handling Conventions

Other considerations for data analyses and data handling conventions are outlined in the appendices:

Section	Component
10.3	Appendix 3: Assessment Windows
10.4	Appendix 4: Study Phases and Treatment Emergent Adverse Events
10.5	Appendix 5: Data Display Standards & Handling Conventions
10.6	Appendix 6: Derived and Transformed Data
10.7	Appendix 7: Reporting Standards for Missing Data
10.8	Appendix 8: Values of Potential Clinical Importance

6. STUDY POPULATION ANALYSES: GROUP 1

6.1. Overview of Planned Study Population Analyses

The study population analyses will be based on the Safety & Enrolled population, with screen failures as an exception.

Study population analyses including analyses of subject's disposition, protocol deviations, demographic and baseline characteristics, prior and concomitant medications, and exposure and treatment compliance will be based on GSK Core Data Standards.

Details of the planned displays are provided in [Appendix 10: List of Data Displays](#) and will be based on GSK data standards and statistical principles.

7. SAFETY ANALYSES: GROUP 1

The safety analyses will be based on the Safety population, unless otherwise specified.

7.1. Adverse Events Analyses

Adverse events analyses including the analysis of adverse events (AEs), Serious (SAEs) and other significant AEs will be based on GSK Core Data Standards. The details of the planned displays are provided in [Appendix 10: List of Data Displays](#).

7.2. Clinical Laboratory Analyses

Laboratory evaluations including the analyses of Chemistry laboratory tests, Hematology laboratory tests, Urinalysis, and liver function tests will be based on GSK Core Data Standards. The details of the planned displays are in [Appendix 10: List of Data Displays](#).

7.3. Other Safety Analyses

The analyses of non-laboratory safety test results including ECGs and vital signs will be based on GSK Core Data Standards, unless otherwise specified. The details of the planned displays are presented in [Appendix 10: List of Data Displays](#).

8. PHARMACOKINETIC ANALYSES : GROUP 1

8.1. Primary Pharmacokinetic Analyses : Group 1

8.1.1. Endpoint / Variables : Group 1

- Plasma concentration time profile for IH oxytocin and 10 I.U. IM oxytocin.
- PK parameters: Maximum observed plasma concentration (C_{max}), Observed plasma concentrations at 10 minutes (min) postdose (C_{p10}), Observed plasma concentrations at 20 min post-dose (C_{p20}), Observed plasma concentrations at 30 min post-dose (C_{p30}), Time to C_{max} (t_{max}), Area under concentration-time curve (AUC(0-t)), and time of last quantifiable concentration will be calculated as data permit.

8.1.1.1. Drug Concentration Measures : Group 1

Refer to [Appendix 5: Data Display Standards & Handling Conventions](#) (Section [10.5.2](#) and Section [10.5.3](#) Reporting Standards for Pharmacokinetic)

8.1.1.2. Derived Pharmacokinetic Parameters: Group 1

Pharmacokinetic parameters will be calculated by standard non-compartmental analysis according to current working practices and GSK procedures using the currently supported version of WinNonlin. All calculations of non-compartmental parameters will be based on actual sampling times. Pharmacokinetic parameters listed will be determined from the plasma concentration-time data, as data permits.

Treatment	Parameter	Parameter Description
IH/IM	C _{max}	Maximum observed concentration, determined directly from the concentration-time data.
IH/IM	C _{p10}	Quantified concentration in PK sample collected at 10 minutes (nominal time) post-dose, determined directly from the concentration-time data.
IH/IM	C _{p20}	Quantified concentration in PK sample collected at 20 minutes (nominal time) post-dose, determined directly from the concentration-time data.
IH/IM	C _{p30}	Quantified concentration in PK sample collected at 30 minutes (nominal time) post-dose, determined directly from the concentration-time data.
IH/IM	t _{max}	Time to reach C _{max} , determined directly from the concentration-time data.
IH/IM	AUC(0-t)	Area under the concentration-time curve from time zero to the time of the last quantifiable concentration (C(t)) will be calculated using the linear trapezoidal rule for each incremental trapezoid and the log trapezoidal rule for each decremental trapezoid.
IH/IM	t _{last}	Time of last quantifiable concentration

At least 2 quantifiable (3 including time 0 where NQ values at time zero will be set to 0) values per profile are required to calculate the AUC(0-t). For profiles with less than 2 quantifiable values, AUC(0-t) will be coded with NC in the PKPar file.

8.1.2. Summary Measure: Group 1

Pharmacokinetic concentration data will be presented in graphical and/or tabular form and will be summarized descriptively by IH oxytocin and IM Oxytocin.

The conversion factor to normalise IM doses is 1 IU = 1.7 mcg oxytocin

As a large number of PK parameter values will be reported as Non Calculable (NC: PK parameter cannot be derived due to the presence of non-quantifiable data) then the PK parameter will be summarised by following measures

- number of subjects with non-missing observations, n, (includes those reported as NC)
- number of subjects for whom parameter cannot be derived because of NQ concentrations, n*, (reported as NC)
- median, minimum and maximum

In addition a frequency table of the number of subjects with all concentrations NQ and the number of subjects with one, or 2 or more measurable concentrations will be produced.

8.1.3. Population of Interest : Group 1

The primary pharmacokinetic analyses will be based on the Pharmacokinetic population, unless otherwise specified.

8.2. POPULATION PHARMACOKINETIC (POPPK) ANALYSES

PK samples will be analysed periodically throughout the study duration to enable development of a preliminary population PK model. If appropriate, a population PK analysis may also be conducted on the final data. In addition the oxytocin plasma concentration-time data may be merged with historical data and analysed as part of a population PK meta-analysis. The timeline for these analyses will be independent of the analysis described in this RAP. To support this analysis a NONMEM-specific data file will be generated, the specifications of which are provided in POP PK RAP appendix.

8.3. Secondary Pharmacokinetic Analyses: Group 1

8.3.1. Endpoint / Variables : Group 1

- Cmax, Cp10, Cp20, Cp30, Area under the concentration-time curve from time zero (pre-dose) to three hours (h) (AUC[0-3h]) will be compared as data permit.

Due to sparse PK concentrations, it is not possible to include a formal statistical analysis to compare IH and IM Oxytocin therefore no statistical analysis will be performed.

8.4. Exploratory Pharmacodynamic Analyses: Group 1

8.4.1. Endpoint / Variables: Group 1

- Pre and post-delivery haemoglobin
- Questionnaire results from participants

8.4.2. Summary Measure: Group 1

Pre and post-delivery Haemoglobin will be summarized and listed along with other haematology parameters. A box plot will be produced for pre and post-delivery haemoglobin.

A listing and a summary table will be produced for the questionnaire results from the Rotahaler.

8.4.3. Population of Interest: Group 1

The exploratory analyses will be based on the Safety population, unless otherwise specified.

10. APPENDICES

**10.1. Appendix 1: Protocol Deviation Management and Definitions
for Per Protocol Population**

This section is not applicable as Per Protocol Population is not defined for this study.

10.2. Appendix 2: Schedule of Activities

10.2.1. Protocol Defined Schedule of Events : Group 1

10.2.1.1. Time & Events General Overview

Group 1

Procedure	Study Day			
	Screening ⁴	Main Phase	Follow – Up 1 (approx. 24 hours post dose)	Follow – Up 2 (7-14 days post dose)
Informed Consent and Demography	X			
Brief Physical Examination	X			
Medical history (incl. substance abuse)	X			
Inhaler device training / education session	X			
Laboratory assessments ¹	X			
Vital signs ²	X	X		
Pharmacokinetic blood sample		X		
Oxytocin Administration (IM/IH)		X		
Full blood count		X		
Labour Events Documentation		X		
Device acceptability questionnaire ³		X		
Prior / concomitant medication review	X	X	X	X
AE review		----- continuous review -----		
SAE review		----- continuous review -----		

1. Only required if done as part of routine care. Additional study-specific laboratory assessments not required.
2. Includes blood pressure, heart rate, temperature, respiratory rate
3. Only to be used when randomized to IH oxytocin
4. To be completed after 18th week of pregnancy (based on estimated date of delivery).

10.2.1.2. Time & Events - Main Phase Procedures

Group 1

Procedure	Pre-dose	Time post dose										
		3 min	5 min	10 min	15 min	20 min	30 min	1 hr	2 hr	2.5 hr	3 hr	4 hr
Vital signs ¹							X		X			
Pharmacokinetic blood sample	X ²	X	X	X	X	X	X	X	X	X	X	X
Prior medication review	X											
Concomitant medication review		----- continuous review -----										
AE review		----- continuous review -----										
SAE Review		----- continuous review -----										
Device Acceptability Questionnaire ³												X
Full Blood Count	X											X

1. Includes blood pressure, heart rate, temperature, respiratory rate
2. Predose PK sample to be taken immediately prior to administration of study treatment
3. Only to be administered when randomized to IH oxytocin

10.3. Appendix 3: Assessment Windows

No assessment windows will be applied.

10.4. Appendix 4: Study Phases and Treatment Emergent Adverse Events

10.4.1. Study Phases

Assessments and events will be classified according to the time of occurrence relative to study treatment.

Study Phase	Definition
Pre-Treatment	Date < Study Treatment Start Date
On-Treatment	Study Treatment Start Date ≤ Date ≤ Study Treatment Stop Date +1
Post-Treatment	Date > Study Treatment Stop Date +1

10.4.1.1. Study Phases for Concomitant Medication

Study Phase	Definition
Prior	If medication end date is not missing and is prior to 18th week of pregnancy.
Concomitant	Any medication that is not a prior

NOTES:

- Please refer to [Appendix 7: Reporting Standards for Missing Data](#) for handling of missing and partial dates for concomitant medication. Use the rules in this table if concomitant medication date is completely missing.

10.4.2. Treatment Emergent Flag for Adverse Events

Flag	Definition
Treatment Emergent	

• If AE onset date is on or after treatment start date & on or before treatment stop date.
• Study Treatment Start Date ≤ AE Start Date ≤ Study Treatment Stop Date +1.

NOTES:

- If the study treatment stop date is missing, then the AE will be considered to be On-Treatment.
- Time of study treatment dosing and start/stop time of AEs should be considered, if collected.

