2.3. Study Design

Overview of Study Design and Key Features	

Group 1 – Women in TSL
  
Group 2 – Non-pregnant, non-lactating females of child bearing potential
 	
Design Features	
 Group 1: This is an open-label, randomized, single dose study enrolling women in the third stage of labour who will receive either IH or IM oxytocin Group 2: This is an open-label, randomized, two dosing, cross over study enrolling healthy, non-pregnant, non-lactating female subjects of childbearing potential who will receive IH oxytocin at one dosing session and IV oxytocin at the other dosing session. It will be divided into two cohorts: Cohort A will enrol women on a combined oral contraceptive. Cohort B will enrol women who are not using a hormonal form of contraceptive.
Dosing	
 Group 1: Subjects will receive 400 mcg IH oxytocin or 10 I.U. IM oxytocin in one dosing session. Follow Up 1 within approximately 24 hours post dose. Follow Up 2 at least 7 days and no greater than 14 days after study drug administration. Total duration: Screening after 18th week of pregnancy (i.e. within 168 days of 1 dosing session) + follow up of 7 - 14 days = approximately 183 days Group 2: Subjects will receive 400 mcg IH oxytocin and 5 I.U. IV oxytocin in two dosing sessions. Follow Up will take place at least 7 days and no greater than 21 days after last study drug administration. Total duration: Screening within 28 days of dosing session 1 + 2 dosing sessions with a maximum of 14 days between dosing + follow-up of 7 – 21 days = 64 days
Time & Events	
 [Refer to Appendix 2: Schedule of Activities]
Treatment Assignment	
 Group 1: Subjects will be randomised to receive one of the following study treatments: A: 400 mcg IH oxytocin B: 10 I.U. IM oxytocin Group 2: Subjects will receive both of the following study treatments over the course

Overview of Study Design and Key Features	
	of two dosing sessions: C: 400 mcg IH oxytocin D: 5 I.U. IV oxytocin

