10.4. Appendix 4: Study Phases and Treatment Emergent Adverse Events

10.4.1. Study Phases

Assessments and events will be classified according to the time of occurrence relative to study treatment.

Study Phase	Definition
Pre-Treatment	Date ≤ Study Treatment Start Date
On-Treatment	Study Treatment Start Date ≤ Date ≤ Study Treatment Stop Date
Post-Treatment	Date > Study Treatment Stop Date

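### Group 1 gives the treatment-emergent flag two different end dates, and Group 2's phase table puts the treatment start date in two phases at once

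*SAP*

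**What the plan says.** The SAP file holds two plans, one per group, each with its own Appendix 4.

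**Group 1, section 10.4.2** defines the treatment-emergent flag in two bullets. The first is "If AE onset date is on or after treatment start date & on or before treatment stop date". The second is "Study Treatment Start Date ≤ AE Start Date ≤ Study Treatment Stop Date +1". No connecting word or order of precedence is given. A note adds that dosing and event times should be taken into account where they were collected.

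**Group 1, section 10.4.1** defines the phases. Pre-treatment is "Date < Study Treatment Start Date" and on-treatment is "Study Treatment Start Date ≤ Date ≤ Study Treatment Stop Date +1".

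**Group 1, section 2.3** describes the design: "This is an open-label, randomized, single dose study enrolling women in the third stage of labour who will receive either IH or IM oxytocin". It places the first follow-up as "Follow Up 1 within approximately 24 hours post dose".

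**Group 2, section 10.4.1** defines pre-treatment as "Date ≤ Study Treatment Start Date" and on-treatment as "Study Treatment Start Date ≤ Date ≤ Study Treatment Stop Date". The table covers assessments as well as events.

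**Group 2, section 10.4.2** assigns adverse events by dosing period: those after the first dosing and before the second belong to Period 1, those after the second belong to Period 2. It carries the same conditional note on clock times.

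**The concern.** A derivation rule should give one answer for each record. In Group 1 two programmers can follow section 10.4.2 faithfully and set different flags for the same event. One choice also breaks the link with the phase table: an event could be on-treatment and yet not treatment-emergent. The note on missing stop dates in the same section treats the two ideas as linked, so they were presumably meant to agree.

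In Group 2 the start date carries both pre-dose procedures and post-dose ones from 2 minutes to 4 hours (section 10.2.1.2). A post-dose record on that date therefore also meets the pre-treatment definition.

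Safety is a secondary objective in Group 1 and a primary objective in Group 2, so these labels should be reproducible.

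**Working it through.** The plan gives no figure to reproduce. The check applies the written date rules day by day, with day 0 as the start date.

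**Group 1.** Input: single dose (section 2.3), hence stop date = start date = day 0. Bullet 1 is 0 ≤ day ≤ 0. Bullet 2 is 0 ≤ day ≤ 0 + 1. The phase rules are those of section 10.4.1.

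| Day of onset | Bullet 1 | Bullet 2 | Phase |
|---|---|---|---|
| −1 | no | no | pre |
| 0 | yes | yes | on |
| 1 | **no** | **yes** | on |
| 2 | no | no | post |

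The bullets differ on day 1 only, and there bullet 2 agrees with the phase table while bullet 1 does not. Day 1 is not remote: an event starting 24 hours after dosing always carries the next calendar date.

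For earlier onsets the chance of crossing midnight depends on the time of delivery, which the document does not give. If delivery times are assumed uniform over the day, the share of events at *h* hours post-dose that fall on day 1 is *h*/24: 4/24 = 17%, 6/24 = 25%, 12/24 = 50%. These illustrate how the date boundary works. They are shares of events at a chosen delay, not of all adverse events.

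**Group 2.** Input: pre-treatment is day ≤ 0, on-treatment is 0 ≤ day ≤ stop, post-treatment is day > stop. The plan does not say whether start and stop are set per session, so three stop dates were tried: 0 (per session), and 2 and 14 (one pair spanning both sessions, from the minimum of 48 hours and maximum of 14 days between sessions in section 2.3).

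| Day | Stop = 0 | Stop = 2 | Stop = 14 |
|---|---|---|---|
| −1 | pre | pre | pre |
| 0 | **pre and on** | **pre and on** | **pre and on** |
| 1 | post | on | on |
| stop | as day 0 | on | on |
| stop + 1 | post (as day 1) | post | post |

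Day 0 falls in two phases under every reading, and no other date does. If the dates are per session, the whole on-treatment phase consists of a date that is also pre-treatment. Group 1's strict inequality for pre-treatment avoids the overlap.

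**The case against.** **The clock-time notes settle it.** In part. Where times were collected they can order a dosing-day event against the dose. But the notes are conditional, they sit under the adverse-event flag and not under the phase table, and no clock time can choose between stop date and stop date + 1.

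**The intended Group 1 rule is recoverable.** The extra day appears in bullet 2 and in both the on-treatment and post-treatment rows of section 10.4.1; only bullet 1 lacks it. It does look like a leftover line. That identifies the fix but leaves the contradiction in the text.

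**Group 2 assessments are separated in practice.** Scheduled time points distinguish pre-dose from post-dose, and baseline is the latest pre-dose value (section 5.2). This limits the harm, but the phase table as written does not use those time points.

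**Stronger readings do not stand.**

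- *Events are dropped from the safety tables.* The lead displays cover all adverse events. No title or programming note in Group 1 Tables 3.17–3.22 and Listings 45–48, or Group 2 Tables 3.1–3.6 and Listings 11–14, restricts to treatment-emergent or on-treatment events. Whether the standard shells filter on the flag cannot be seen here.
- *Group 2's attribution of adverse events is contradictory.* Section 10.4.2 of that plan assigns events by period without overlap and does not depend on the phase table.
- *A next-day event in Group 2 is on-treatment after session 1 but post-treatment after session 2.* This follows only if one start and stop pair spans both sessions, which the plan does not say. Under the period rule such an event goes to its own session either way.

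**Conclusion.** Both inconsistencies are present in the text. In Group 1, the two end dates give opposite flags for every adverse event starting on the calendar day after dosing and agree on all other days; only stop date + 1 is consistent with section 10.4.1. This rests on the single-dose design. In Group 2, the treatment start date belongs to two phases whichever way start and stop are defined, so phase labels on that date are not unique.

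The effect is confined to the flag and the phase labels. A reader might take the 17%, 25% and 50% as the proportion of adverse events affected, but the document contains no data on event timing that would support this. Safety reporting is descriptive and no formal hypothesis depends on these rules. The correction is nevertheless worth making, because the rules as written cannot be programmed unambiguously and the remedy is simple.

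**What to change.** **Group 1, section 10.4.2.** Delete the first bullet and keep "Study Treatment Start Date ≤ AE Start Date ≤ Study Treatment Stop Date +1" as the only definition, matching section 10.4.1. Where clock times were collected, use them to exclude onsets before the dose.

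**Group 2, section 10.4.1.** Make the phases mutually exclusive in one of two ways:

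- Use the Group 1 form for pre-treatment, "Date < Study Treatment Start Date". Each date then has one label, though pre-dose records on the start date become on-treatment.
- Split **both** the pre-treatment and on-treatment rows at the dosing time or scheduled time point. Changing only the pre-treatment row to a date-time is not enough: a pre-dose record on the dosing date would still satisfy the date-based on-treatment row.

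Also state whether start and stop dates are per session or span both sessions, and align the phase table with the period rule in section 10.4.2 of the Group 2 plan.

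**Cost.** A wording change in two appendices and the matching derivation code. The date-based versions need no new data; a split by clock time depends on times having been recorded, which the plan treats as conditional.

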10.5. Appendix 5: Data Display Standards & Handling Conventions

10.5.1. Reporting Process

Software	

 The currently supported versions of SAS software 9.4 will be used. 	
Reporting Area	
HARP Server	: UK1SALX00175
HARP Compound (Group 1 Dry Run)	: /arenv/arprod/gr121619/mid205920/final_03
HARP Compound (Group 1 Final)	/arenv/arprod/gr121619/mid205920/final_04
Analysis Datasets	

 Analysis datasets will be created according to Legacy GSK A&R dataset 	
Generation of RTF Files	

 RTF files will be generated for summary tables 	

10.5.2. Reporting Standards

General	

 The current GSK Integrated Data Standards Library (IDSL) will be applied for reporting, unless otherwise stated (IDSL Standards Location: https://spope.gsk.com/sites/IDSLLibrary/SitePages/Home.aspx): 
 4.03 to 4.23: General Principles 5.01 to 5.08: Principles Related to Data Listings 6.01 to 6.11: Principles Related to Summary Tables 7.01 to 7.13: Principles Related to Graphics 	
Formats	

 All data will be reported according to the actual treatment the subject received unless otherwise stated. GSK IDSL Statistical Principles (5.03 & 6.06.3) for decimal places (DP's) will be adopted for reporting of data based on the raw data collected, unless otherwise stated. Numeric data will be reported at the precision collected on the eCRF. The reported precision from non eCRF sources will follow the IDSL statistical principles but may be adjusted to a clinically interpretable number of DP's. 	
Planned and Actual Time	

 Reporting for tables, figures and formal statistical analyses: 
 Planned time relative to dosing will be used in figures, summaries, statistical analyses and calculation of any derived parameters, unless otherwise stated. The impact of any major deviation from the planned assessment times and/or scheduled visit days on the analyses and interpretation of the results will be assessed as appropriate. Reporting for Data Listings: 
 Planned and actual time relative to study drug dosing will be shown in listings (Refer to IDSL Statistical Principle 5.05.1). Unscheduled or unplanned readings will be presented within the subject's listings. 	
Unscheduled Visits	

 Unscheduled visits will not be included in summary tables and/or figures. All unscheduled visits will be included in listings. 	

Descriptive Summary Statistics	
Continuous Data	Refer to IDSL Statistical Principle 6.06.1
Categorical Data	N, n, frequency, %
Reporting of Pharmacokinetic Concentration Data	
Descriptive Summary Statistics	Refer to IDSL Statistical Principle 6.06.1 Assign zero to NQ values (Refer to GUI_51487 for further details)
Reporting of Pharmacokinetic Parameters	
Summary table	Summary table will be produced as described in Section 8.1.2
Listing	All PK Parameters that are collected will be listed
Reporting of No treatment	
If in a situation where a subject has received no treatment, then the subject will be included only in Screened and enrolled population.	
Graphical Displays	
Refer to IDSL Statistical Principals 7.01 to 7.13. All figures will use coloured lines	

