10.6. Appendix 6: Derived and Transformed Data

10.6.1. General

Multiple Measurements at One Analysis Time Point

 • Mean of the measurements will be calculated and used in any derivation of summary statistics but if listed, all data will be presented. • Participants having both High and Low values for Normal Ranges at any post-baseline visit for safety parameters will be counted in both the High and Low categories of “Any visit post-baseline” row of related summary tables. This will also be applicable to relevant Potential Clinical Importance summary tables.
Study Day

 • Calculated as the number of days from First Dose Date: 
 • Ref Date = Missing → Study Day = Missing • Ref Date < First Dose Date → Study Day = Ref Date – First Dose Date • Ref Date ≥ First Dose Date → Study Day = Ref Date – (First Dose Date) + 1

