10.10.7. Safety Tables

Safety: Tables					
No.	Population	IDSL / Example Shell	Title	Programming Notes	Deliverable [Priority]
Adverse Events (AEs)					
3.17.	Safety	AE1	Summary of All Adverse Events by System Organ Class and Preferred Term		DR [1], SAC
3.18.	Safety	AE1	Summary of Drug-Related Adverse Events		DR [1], SAC
3.19.	Safety	AE1	Summary of Non-Serious Adverse Events		DR [1], SAC
3.20.	Safety	AE15	Summary of Common (>1 Subject) Non-serious Adverse Events by System Organ Class and Preferred Term (Number of Subjects and Occurrences)	FDAAA, EudraCT	DR [1], SAC
Serious and Other Significant Adverse Events					
3.21.	Safety	AE16	Summary of Serious Adverse Events by System Organ Class and Preferred Term (Number of Subjects and Occurrences)	FDAAA, EudraCT	DR [1], SAC
3.22.	Safety	AE1	Summary of Adverse Events Leading to Permanent Discontinuation of Study Drug or Withdrawal from Study		DR [1], SAC

Safety: Tables					
No.	Population	IDSL / Example Shell	Title	Programming Notes	Deliverable [Priority]
Laboratory: Hematology					
3.23.	Safety	LB1	Summary of Haematology Values		DR [1], SAC
3.24.	Safety	LB1	Summary of Haematology Changes from Baseline		DR [1], SAC
Vital Signs					
3.25.	Safety	VS1	Summary of Vital Signs		DR [1], SAC
3.26.	Safety	VS1	Summary of Change from Baseline for Vital Signs		DR [1], SAC
3.27.	Safety	VS7	Summary of Vital Sign Results Relative to Potential Clinical Importance (PCI) Criteria Post-Baseline Relative to Baseline		DR [1], SAC
Exploratory : Questionnaire Results					
3.28.	Safety	SAFE_T1	Summary of Device Acceptability Questionnaire for Rotahaler Inhaler		DR[1], SAC

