10.2.1.2. Time & Events - Main Phase Procedures

Group 2 - Sessions 1 and 2

Procedure	Pre-dose	Time Post Dose														
		2 min	3 min	5 min	8 min	10 min	15 min	20 min	30 min	45 min	1 hr	1.5 hr	2 hr	2.5 hr	3 hr	4 hr
Brief Physical Exam	X															
Pregnancy Test	X															
Alcohol Breath Test, Smokerlyzer, Urine Drug Screen ¹	X															
Vital signs ²	X			X			X		X		X					X
12-lead ECG	X	X				X		X	X		X					X
Cardiac Telemetry		-----Continuous-----														
Spirometry ³	X											X				
Pharmacokinetic blood sample	X ⁵	X	X	X	X	X	X	X	X	X	X	X	X	X	X	X
Immunogenicity Sample	X															
Laboratory assessments (including liver chemistries)	X															X
Prior medication review	X															
Concomitant medication review		-----continuous review-----														
AE review		-----continuous review-----														
SAE Review		-----continuous review-----														
Discharge from unit ⁴																X

1. Smokerlyzer at Principal Investigator (PI)/designee discretion if smoking history in question.
2. Includes blood pressure, heart rate, temperature, respiratory rate, and SpO2
3. FEV 1.0 will be performed in triplicate at each time point. Record all three values on source document, and record best effort in eCRF.
4. Discharge at PI discretion, no sooner than 4-hours post-dose.
5. 3 pre-dose samples: approximately 1 hr pre-dose, 30 minutes pre-dose, and 15 minutes pre-dose

CONFIDENTIAL

205920

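### Read naturally, both RAPs leave off-schedule vital signs out of the potential-clinical-importance tables (3.27 and 3.16), so those counts can be too low

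*SAP*

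**What the plan says.** The SAP file holds two reporting and analysis plans (RAPs), one per group. Section 10.5.2 is worded alike in both on this point:

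- On summaries: "Unscheduled visits will not be included in summary tables and/or figures".
- On listings: "All unscheduled visits will be included in listings", and, in a separate line, "Unscheduled or unplanned readings will be presented within the subject's listings".
- On the time basis: "Planned time relative to dosing will be used in figures, summaries, statistical analyses and calculation of any derived parameters, unless otherwise stated".

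The PCI display for vital signs has the same title in both plans: "Summary of Vital Sign Results Relative to Potential Clinical Importance (PCI) Criteria Post-Baseline Relative to Baseline". It is Table 3.27 in section 10.10.7 of the Group 1 RAP and Table 3.16 in the same section of the Group 2 RAP. The programming note for 3.27 is blank and that for 3.16 asks only for a split by cohort, so neither mentions unscheduled values.

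Section 10.6.1 of both plans deals with "Participants having both High and Low values for Normal Ranges at any post-baseline visit for safety parameters". It counts such women in both the high and the low category of a row for any visit after baseline, and extends this to the relevant PCI tables. It does not say whether unscheduled values feed that row.

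**The concern.** Leaving unscheduled values out is sensible for a table of means by time point, where an extra reading has no column. A PCI table asks a different question: did this woman cross a limit at any time after baseline? An extra reading is directly relevant to that, and it may have been taken because something looked wrong. Applying the same exclusion to both kinds of table means the display meant to show out-of-limit values may omit some of them.

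Safety and tolerability is a secondary objective in Group 1 and a primary objective in Group 2, and section 2.2 names vital signs among the endpoints for both. The Group 1 schedule makes the point sharper, because it has few post-dose vital sign times and none early.

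**Working it through.** The plan gives no figure to reproduce. The check is to set the schedules and reporting rules side by side.

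**1. Scheduled post-dose vital signs (section 10.2.1.2 of each RAP).**

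| | Scheduled post-dose times | Before 30 min |
|---|---|---|
| Group 1 ("Includes blood pressure, heart rate, temperature, respiratory rate") | 30 min, 2 hr | 0 of 2 |
| Group 2 ("Includes blood pressure, heart rate, temperature, respiratory rate, and SpO2") | 5, 15, 30 min, 1 hr, 4 hr | 2 of 5 |

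The Group 1 general overview (10.2.1.1) schedules no vital signs at either follow-up, so two readings per woman are all that can be tabulated after dosing. The same Group 1 schedule has PK samples at 3, 5, 10, 15 and 20 min, so the plan treats this early period as one of interest. In Group 2 there is no scheduled vital sign between 1 hr and 4 hr.

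**2. Where an off-schedule reading goes.** It has no planned time, so the planned-time rule gives it no slot in a summary. The unscheduled-visit rule keeps unscheduled data out of summary tables. Listings are the only place named for unplanned readings. No exemption is attached to Table 3.27 or 3.16. A programmer following these lines would leave it out.

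**3. Direction of the effect.** Let S be a woman's scheduled post-baseline readings and U her unscheduled ones. She is flagged on all data if any reading in S or U crosses a limit, and on scheduled data if any reading in S does. Every woman flagged on S is also flagged on S and U together, so dropping U gives a count that is equal or lower, never higher.

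**4. Illustration (invented readings).** The systolic limit is below 85 mmHg (10.8.2 in Group 1, 10.8.3 in Group 2). A Group 1 woman with 78 mmHg at 8 min, off schedule, and 92 mmHg at 30 min crosses the limit on all data. On scheduled data she does not, provided her 2 hr reading is also within limits.

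**5. Size per woman missed.** The understatement is 1/n in an arm of n. The SAP gives no arm size for these tables, so n is assumed to lie between 5 and 20:

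- n = 5: 1/5 = 20 percentage points
- n = 20: 1/20 = 5 percentage points

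How many women would be missed cannot be worked out from the document.

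**The case against.** **The text bars visits, not readings.** An extra blood pressure on the dosing day falls within the scheduled main phase, and 10.5.2 mentions unplanned readings separately, only to send them to listings. The planned-time rule also allows exceptions. This stands in part: exclusion is the natural reading but is not stated outright. Against it, section 5.2 of the Group 1 RAP speaks of unscheduled visits within a rule about choosing the latest pre-dose assessment, which suggests the word covers individual measurements there.

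**Nothing is lost.** This stands. Group 1 Listing 50 shows all vital signs with PCI flags. Group 2 Listing 24 shows the PCI values, and Listing 23 shows all vital signs for the women concerned. With few women these can be read in full. A listing does not, however, correct a table that reports too few women.

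**The early gap comes from the schedule.** True: the reporting rule did not create it, and the document does not show that vital signs are taken before 30 min in Group 1. The rule matters only if such readings exist.

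**Including the readings has its own bias.** Women measured more often have more chances to be counted, and in an open-label study that could differ by arm. This stands, and the fix makes it visible. Some unscheduled readings will also be repeats after an abnormal scheduled value; leaving those out does not change whether the woman is counted.

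Two stronger readings are tempting but unsupported:

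- *Early safety events cannot be counted in any safety summary.* The adverse event and serious adverse event tables (3.17 to 3.22; 3.1 to 3.6) are not built on scheduled times, and adverse events are reviewed continuously after dosing. The limitation concerns vital sign tables only.
- *The averaging rule in 10.6.1 is a second error, because a low reading and its repeat can average back within limits.* That rule concerns the derivation of summary statistics. It does not say PCI limits are applied to means, and no replicate vital signs are scheduled.

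**Conclusion.** The concern holds in limited form. Neither RAP gives an off-schedule post-dose vital sign a route into Table 3.27 or 3.16, and 10.5.2 is not reconciled with the any-visit-post-baseline row in 10.6.1. On the natural reading the PCI counts can be understated and cannot be overstated by this rule. In Group 1 no vital sign before the 30 min reading could be counted.

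The size is 1/n per woman missed. This rests on three assumptions: that unscheduled visits is read to cover single readings, that some off-schedule readings were taken, and that arms hold 5 to 20 women. The document does not establish that any woman would in fact be missed. This is a rule worth correcting for two tables, not a failure of safety reporting as a whole.

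**What to change.** In 10.5.2 of both RAPs, replace the blanket exclusion with wording such as: *Unscheduled post-baseline readings are left out of by-time-point summaries but are included in the PCI summaries for vital signs (Table 3.16 or 3.27), in the row for any visit post-baseline.*

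Add a footnote to each table giving the number of women with unscheduled readings per arm (in Group 2, per treatment within cohort). In 10.6.1, state that the any-visit-post-baseline row takes both scheduled and unscheduled readings, so that the two sections agree.

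The cost is a few lines of text and a small programming change, using data the listings already require. No assessment or schedule changes. The drawback is that more frequent measurement gives more chances to be counted; the footnote lets the reader judge this.
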